7.6 Early study termination by the sponsor

The study can be terminated by Novartis at any time for any reason. This may include reasons related to the benefit/ risk assessment of participating in the study, practical reasons (including slow enrollment), or for regulatory or medical reasons. Should this be necessary, patients must be seen as soon as possible and treated as a prematurely withdrawn patient. The investigator may be informed of additional procedures to be followed in order to ensure that adequate consideration is given to the protection of the patient's interests. The investigator will be responsible for informing IRBs/IECs of the early termination of the trial.

8 Procedures and assessments

8.1 Assessment schedule

Assessment Schedule

EPOCH	SCREENING		Treatment															
	Visit Name	Screening	Baseline ²⁵	Treatment														
Visit Numbers ¹	1	2	101					102 ³	103 ³	104 ³	105					106 ³	107 ³	199
Study Day(s)	-60 to -15	-14/-20 to -1	1					7 -2 +2	14 -2 +2	28 -2 +2	42 -2 +2					56 -2 +2	84 -2 +2	112 -2 +2
Time (post-dose)	-	-	0h ³	1h	2h	4h ⁴	6h	-	-	-	0h ³	1h	2h	4h ⁴	6h	-	-	-
Informed consent ⁵	X																	
Corporate Confidential Information	X																	
Inclusion / Exclusion criteria	X	X																
Medical history/current medical conditions	X	X																
Demography	X																	
Alcohol Test and Drug Screen	X	X																
Hepatitis and HIV Screen	X																	
Pregnancy test ⁷	X	X	X							X						X	X	X
Physical examination	X	X								X						X	X	X
Body height	X																	
Body weight	X	X								X	X					X	X	X
Waist and Hip circumference	X	X								X	X					X	X	X
Body temperature	X	X														X	X	X
Blood Pressure and Pulse Rate ^{8,9}	X	X							X	X						X	X	X
ECG evaluation	X	X	X	X	X	X	X	X	X	X	X	X	X	X	X	X	X	X
Hematology	X	X	X					X	X	X	X					X	X	X
Blood chemistry	X	X	X					X	X	X	X					X	X	X

¹ Visit structure given for internal programming purpose only

² If a patient withdraws from the study, or if study medication is discontinued for any reason, the patient should be scheduled for a subsequent visit at which time all assessments at the EOS visit should be performed.

³ Assessments to be performed pre-dose

⁴ A meal will be provided 4 hours post dose.

⁵ Informed consent must be provided by all patients before any screening procedures are performed. The pharmacogenetic assessment is optional and requires a separate informed consent to be signed

Corporate Confidential Information

⁷ Serum pregnancy tests will be performed at Screening and end of study; urine tests may be used at other timepoints.

⁸ At screening and baseline, if vital signs are out-of-range, the investigator may obtain two additional readings, so that up to three (3) consecutive assessments are made, each after at least 30 minutes, and with the patient seated quietly during the five (5) minutes preceding the assessment. At least the last reading must be within the ranges provided in order for patients to qualify.

⁹ Blood pressure and pulse rate will be measured in a sitting position at all visits.

¹⁰ Lipid panel includes total cholesterol, LDL, HDL (including subfractions HDL-1, HDL-2, and HDL-3), and Triglycerides. Direct LDL will also be measured pre-dose at V101, V105, V107, and EOS (V199). Additional analyses of LDL sub-fraction and ApoC3 at these timepoints may be performed if notable changes in LDL or triglycerides, respectively, are observed.

¹¹

Corporate Confidential Information

²² Patients will be provided with a supply of study medication to self-administer once daily for 12 weeks (Day 2 to Day 84). Study medication will be administered by site personnel on all visit days. Patients should bring all used and unused medications, and diaries, to each visit.

²³ MRI of the abdomen, including liver; see Imaging manual for further instructions.

²⁴ A thorough review of any concomitant medications (including medication name, dose, unit, frequency, and route) should be performed at every visit.

²⁵ Baseline period is 14 days for Cohort 1, and 20 days for Cohort 2.

8.2 Informed consent procedures

Eligible patients may only be included in the study after providing (witnessed, where required by law or regulation), IRB/IEC-approved informed consent.

Novartis will provide to investigators a proposed informed consent form that complies with the ICH E6 GCP guideline and regulatory requirements and is considered appropriate for this study. The informed consent form will also include a section related to optional future research which will require a separate signature if the patient agrees to future research. Any changes to the proposed consent form suggested by the investigator must be agreed to by Novartis before submission to the IRB/IEC.

Information about common side effects already known about the investigational drug can be found in the Investigator's Brochure (IB). This information will be included in the patient informed consent and should be discussed with the patient during the study as needed. Any new information regarding the safety profile of the investigational drug that is identified between IB updates will be communicated as appropriate, for example, via an Investigator Notification or an Aggregate Safety Finding. New information might require an update to the informed consent and then must be discussed with the patient.

Ensure patients are informed of the contraception requirements outlined in the [Section 4.2](#) (Exclusion criteria) and in [Section 5.1](#) (Contraception requirements).

Corporate Confidential Information

A copy of the approved version of all consent forms must be provided to the Novartis monitor after IRB/IEC approval.

8.3 Patient screening

In general it is permissible to re-screen a patient if he/she fails the initial screening; however, each case must be discussed and agreed with the Sponsor on a case-by-case basis.

Information on what data should be collected for screening failures is outlined in the Site Operations Manual.

8.4 Patient demographics/other baseline characteristics

Patient demographic and baseline characteristic data will be collected on all patients. Relevant medical history/current medical conditions data will also be collected until signature of informed consent. Details are outlined in the Site Operations Manual.

Investigators have the discretion to record abnormal test findings on the medical history CRF, if in their judgment, the test abnormality occurred prior to the informed consent signature.

8.4.1 Hepatitis screen, HIV screen

All patients will be screened for HIV, Hepatitis B and C. See the Site Operations Manual for details.

8.4.2 Alcohol test, Drug screen

All patients will be screened substances of abuse and cotinine. See the Site Operations Manual for details.

8.5 Efficacy / Pharmacodynamics

Efficacy of LMB763 will be assessed based on the following assessments:

- Liver function tests (ALT)
- Magnetic Resonance Imaging (MRI)
- Anthropometric assessments
- Markers of liver fibrosis
- Fasting lipids
- Visual Analog Scale (VAS) for Itch

Pharmacodynamic samples will be collected at the timepoints defined in the [Assessment schedule](#). Follow instructions outlined in the central laboratory manual regarding sample collection, numbering, processing and shipment. In order to better define the PD profile, the timing of the sample collection may be altered based on emergent data. The number of samples/blood draws and total blood volume collected will not exceed those stated in the protocol. Pharmacodynamic (PD) samples will be obtained and evaluated in all patients at all dose levels.

8.5.1 Liver function tests (LFTs)

ALT, AST, GGT, ALP (total), total bilirubin, and albumin will be assessed as indicated in the [Assessment Schedule](#). The effect on circulating ALT levels is the primary efficacy variable for this study.

If the total bilirubin concentration is increased above 1.5 times the upper limit of normal, direct and indirect reactive bilirubin will be quantified.

ALP isoenzymes and 5'NT will also be measured but will not form part of the screening requirements or safety data set.

The methods for assessment and recording are specified in the laboratory manual. Some of the liver function tests may be completed as part of the blood chemistry panel.

8.5.2 Magnetic Resonance Imaging

Patients will undergo magnetic resonance imaging twice during the course of the study (Baseline and End of Treatment) to quantitate liver fat. Optional exploratory MRI based assessments will be performed in a subset of patients to evaluate the effect of LMB763 on other MRI related endpoints as outlined in [Section 8.1 \(Assessment schedule\)](#). All patients who discontinue prematurely must have an end of treatment MRI assessment.

8.5.3 Markers of Liver Fibrosis

- Fibroscan[®] (Optional): will be performed where available to assess liver stiffness (in kPa). If Fibroscan is unavailable, alternative technology to assess liver stiffness may be considered upon consultation with the sponsor
- Enhanced liver fibrosis Test (ELF) panel: the following will be assessed: hyaluronic acid (HA), tissue inhibitor of metalloproteinases (TIMP-1), and amino-terminal pro-peptide of procollagen type III (PIIINP)
- Fibrosis biomarker test (originally called Fibrotest[®]/ Fibrosure[®]): the following will be assessed: α 2-macroglobulin, apolipoprotein A1, total bilirubin, haptoglobin, GGT, and ALT
- Additional fibrosis markers may be assessed, including but not limited to collagen neo-epitopes, FIB4, APRI and NAFLD scores

Additional information is provided in the site operations manual and central laboratory manual. These markers will be assessed as indicated in [Section 8.1 Assessment schedule](#).

8.5.4 Fasting Lipids

Blood samples will be collected for a fasting lipid panel, including total cholesterol, HDL-cholesterol and LDL-cholesterol, triglycerides, free glycerol and free fatty acids as per [Section 8.1 \(Assessment schedule\)](#). Lipid measurements should be collected under fasted conditions. Detailed information will be provided in the central laboratory manual.

8.5.5 Anthropometric Assessments

Height, body weight (to the nearest 0.1 kilogram [kg] in indoor clothing, but without shoes), and waist and hip circumference in centimeters (cm), will be measured as indicated in [Section 8.1 \(Assessment schedule\)](#). Details of these assessments will be provided in the site operations manual.

8.5.6 Clinical Outcome Assessments (COAs)

Visual Analog Scale (VAS)

10 cm visual analogue scale (VAS) will be used to assess the severity of patients itch (ranging from 0 = no itch at all to 10 = the worst imaginable itch). The score (distance from left) on the VAS will be recorded by the patient marking with a line and used to test for an effect of LMB763 over placebo.

The scale will be completed by patients as indicated in [Section 8.1 \(Assessment schedule\)](#).

8.6 Safety

Safety assessments are specified below; methods for assessment and recording are specified in the Site Operations Manual, with the [Assessment Schedule \(Section 8.1\)](#) detailing when each assessment is to be performed.

8.6.1 Physical examination

See the Site Operations Manual for details.

8.6.2 Vital signs

- Body temperature
- Blood pressure (BP)
- Pulse

8.6.3 Laboratory evaluations

Clinically relevant deviations of laboratory test results occurring during or at completion of the study must be reported and discussed with Novartis personnel. The results should be evaluated for criteria defining an adverse event and reported as such if the criteria are met. Repeated evaluations are mandatory until normalization of the result(s) or until the change is no longer clinically relevant. In case of doubt, Novartis personnel should again be contacted.

Hematology

Hemoglobin, hematocrit, red blood cell count, white blood cell count with differentials and platelet count will be measured.

Coagulation parameters including APTT, PT, and INR will also be assessed; methods for assessment and recording are provided in the central laboratory manual.

Clinical chemistry

Sodium, potassium, creatinine, BUN/urea, uric acid, serum phosphate, chloride, albumin, calcium, alkaline phosphatase, total bilirubin, bicarbonate/HCO₃, LDH, GGT, CK, glucose, total cholesterol, triglycerides.

Liver function tests are outlined in [Section 8.5.1](#).

- Homeostasis model assessment (HOMA)-IR will also be derived, but will not be part of the safety dataset

Urinalysis

Dipstick measurements for specific gravity, albumin, protein, glucose and blood will be performed. Microscopy, WBC, RBC and sediments will also be assessed in case of an abnormal dipstick test.

8.6.4 Electrocardiogram (ECG)

Full details of all procedures relating to the ECG collection and reporting are contained in the site operations manual.

PR interval, QRS duration, heart rate, RR, QT, QTc will be assessed.

The Fridericia QT correction formula (QTcF) (calculated with the RR interval expressed in seconds) should be used for clinical decisions.

Clinically significant abnormalities should be recorded on the relevant medical history CRF page prior to informed consent signature and on the Adverse Events page thereafter. Clinically significant findings must be discussed with the sponsor.

8.6.5 Pregnancy assessments

All pre-menopausal women who are not surgically sterile will have a serum pregnancy test at Screening Visit followed by a urine pregnancy test at Baseline Visit and before study drug administration. The urine pregnancy test will be repeated every four weeks up to the follow up visit where a serum pregnancy test will be repeated. See the [Assessment Schedule, Section 8.1](#), for timing of the protocol required pregnancy testing; additional pregnancy testing may be performed to meet local requirements.

A positive test at Screening Visit and/or Baseline Visit is an exclusion criterion for participating in the study. A positive pregnancy test after start of study drug requires immediate interruption of study drug until serum β -hCG is performed and found to be negative. If positive, the patient will enter the post-treatment follow up period.

If additional pregnancy testing is needed per local requirements, those additional results will be kept as source documentation only.

8.7 Pharmacokinetics

PK samples will be collected at the timepoints defined in the [Assessment schedule, Section 8.1](#). Follow instructions outlined in the central laboratory manual regarding sample collection, numbering, processing and shipment. See [Section 8.9](#) regarding the potential use of residual samples.

Corporate Confidential Information

Concentrations will be expressed in mass per volume units. Concentrations below the LLOQ will be reported as “zero” and missing data will be labeled as such in the Bioanalytical Data Report.

Corporate Confidential Information

9 Safety monitoring

9.1 Adverse events

An adverse event (AE) is any untoward medical occurrence (i.e., any unfavorable and unintended sign [including abnormal laboratory findings], symptom or disease) in a patient or clinical investigation patient *after providing written informed consent* for participation in the study until the end of study visit. Therefore, an AE may or may not be temporally or causally associated with the use of a medicinal (investigational) product.

In addition, all reports of intentional misuse and abuse of the study treatment are also considered an adverse event irrespective if a clinical event has occurred. See [Section 9.5](#) for an overview of the reporting requirements.

The occurrence of adverse events must be sought by non-directive questioning of the patient at each visit during the study. Adverse events also may be detected when they are volunteered by the patient during or between visits or through physical examination finding, laboratory test finding, or other assessments.

Abnormal laboratory values or test results constitute adverse events only if they fulfill at least one of the following criteria:

- they induce clinical signs or symptoms,
- they are considered clinically significant,
- they require therapy.

Clinically significant abnormal laboratory values or test results should be identified through a review of values outside of normal ranges/clinically notable ranges, significant changes from baseline or the previous visit, or values which are considered to be non-typical in patients with underlying disease. Investigators have the responsibility for managing the safety of individual patient and identifying adverse events. Alert ranges for liver and kidney related events are included in [Section 9.3](#) and [Section 9.4](#), respectively.

Adverse events must be recorded on the Adverse Events CRF under the signs, symptoms or diagnosis associated with them, and accompanied by the following information:

1. the Common Toxicity Criteria (CTC) AE grade (version 4.0 or higher) for the adverse event. If CTC-AE grading does not exist for an adverse event, use:
 - 1 = mild,
 - 2 = moderate,
 - 3 = severe
 - 4 = life threatening* (see [Section 9.2](#) for definition of a serious adverse event (SAE))
*Note: There may be cases where a CTCAE with a grade of 4 (life-threatening) may not necessarily be an SAE (e.g. certain laboratory abnormalities in the absence of meeting other seriousness criteria).
 - CTC-AE grade 5 (death) is not used, but is collected as a seriousness criteria and also collected in other CRFs (e.g. Study Completion, Death/Survival).
2. its relationship to the study treatment
 - Yes or
 - No
3. its duration (start and end dates) or if the event is ongoing an outcome of not recovered/not resolved must be reported.
4. whether it constitutes a SAE (see [Section 9.2](#) for definition of SAE) and which seriousness criteria have been met
5. Action taken regarding investigational treatment. All adverse events must be treated appropriately. Treatment may include one or more of the following:
 - no action taken (e.g. further observation only)
 - investigational treatment dosage increased/reduced
 - investigational treatment interrupted/withdrawn
 - concomitant medication or non-drug therapy given
 - hospitalization/prolonged hospitalization (see [Section 9.2](#) for definition of SAE)
6. its outcome (not recovered/not resolved; recovered/resolved; recovering/resolving, recovered/resolved with sequelae; fatal; or unknown).

Information about common side effects already known about the investigational drug can be found in the Investigator's Brochure (IB). Once an adverse event is detected, it must be followed until its resolution or until it is judged to be permanent, and assessment should be made at each visit (or more frequently, if necessary) of any changes in severity, the suspected relationship to the investigational drug, the interventions required to treat it, and the outcome.

The investigator must also instruct each patient to report any new adverse event (beyond the protocol observation period) that the subject, or the patient's personal physician, believes might reasonably be related to study treatment. This information must be recorded in the investigator's source documents; however, if the AE meets the criteria of an SAE, it must be reported to Novartis.

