3.1 Study design

This is a non-confirmatory, multicenter, patient and investigator blinded, randomized, placebo-controlled, parallel group study, in two cohorts, in patients with NASH. The sponsor will remain unblinded to the treatment assignment of all patients to allow for continuous unblinded safety monitoring.

The study will be conducted in two cohorts:

Cohort 1: Corporate Confidential Information
Once eligibility has been confirmed at baseline, approximately 96 patients are planned to be randomized in a 2:1 ratio to receive LMB763 or matching placebo.

[figure not shown]
Cohort 2 Corporate Confidential Information
An additional approximately 96 patients will be randomized in a 2:1 ratio to receive LMB763 or placebo to ensure approximately 81 patients complete the study at this dose level.

All patients who have been enrolled into the initial cohort will complete the protocol at that dose, but no further patients will be recruited into Cohort 1 Corporate Confidential Information

Cohort 1

The study will consist of a 45 day screening period (Day -60 to Day -15), a baseline period of 14 days (Day -14 to Day -1), a treatment period of 12 weeks (Day 1 to Day 84), and a study completion evaluation approximately twenty-eight days after the last drug administration (Day 112 +/- 2 days). Patients will be advised to maintain their recommended diet for NASH during the study. The study design scheme is shown below.

Figure 3-1 Study design – Cohort 1

^a Patients will be randomized in a 2:1 ratio to receive LMB763 100 mg (n ~ 64) or matching Placebo (n ~ 32). Study medication will be self administered by patients once daily for 12 weeks. On visit days, study medication will be administered at the site. If additional dosing arms are included, the same study design will be followed.

^b EOS evaluation to be completed approximately 28 days after the final study drug administration (i.e. Day 112 (± 2 days))

^c Treatment randomization may occur prior to day 1 as soon as patient eligibility is confirmed from baseline assessments

^d All visit during the treatment and follow-up periods will have a window of ± 2 days

Cohort 2

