7.1 Study completion and post-study treatment

Each patient will be required to complete the study in its entirety and thereafter no further study treatment will be made available to them.

Study completion is defined as when the last patient completes their Study Completion visit, and any repeat assessments associated with this visit have been documented and followed-up appropriately by the Investigator, or in the event of an early study termination decision, the date of that decision.

All patients should have a safety follow-up call conducted 30 days after last visit. The information collected is kept as source documentation. All SAEs reported during this time period must be reported as described in [Section 9.2](#) and the Site Operations Manual. Documentation of attempts to contact the patient should be recorded in the source documentation.

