9.2.2 SAE reporting

To ensure patient safety, every SAE, regardless of causality, occurring after the patient has provided informed consent and until 30 days [after the last study visit] must be reported to Novartis **within 24 hours of learning of its occurrence** as described below. Any SAEs experienced after this period should only be reported to Novartis if the investigator suspects a causal relationship to study treatment.

Note: SAEs reported by patients deemed to be screen failures must be reported to Novartis as outlined here with appropriate information also captured in the CRFs as specified in the Site Operations Manual.

All follow-up information for the SAE including information on complications, progression of the initial SAE and recurrent episodes must be reported as follow-up to the original episode within 24 hours of the investigator receiving the follow-up information. An SAE occurring at a different time interval or otherwise considered completely unrelated to a previously reported one must be reported separately as a new event.

Follow-up information provided must describe whether the event has resolved or continues, if and how it was treated, whether the blind was broken or not (if applicable) and whether the patient continued or withdrew from study participation. Each re-occurrence, complication, or progression of the original event must be reported as a follow-up to that event regardless of when it occurs.

If the SAE is not previously documented in the Investigator's Brochure or Package Insert (new occurrence) and is thought to be related to the study treatment a Drug Safety and Epidemiology Department associate may urgently require further information from the investigator for Health Authority reporting. Novartis may need to issue an Investigator Notification (IN) to inform all investigators involved in any study with the same study treatment that this SAE has been reported. Suspected Unexpected Serious Adverse Reactions (SUSARs) will be collected and reported to the competent authorities and relevant ethics committees in accordance with EU Guidance 2011/C 172/01 or as per national regulatory requirements in participating countries.

Follow the detailed instructions outlined in the Site Operations Manual regarding the submission process for reporting SAEs to Novartis. Note: **SAEs must be reported to Novartis within 24 hours** of the investigator learning of its occurrence/receiving follow-up information.

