7.2 Descriptive analyses

Subject demographics and other baseline characteristics

All data for background and demographic variables will be listed by treatment and subject and summarized by treatment.

Relevant medical history, current medical conditions, results of laboratory screens, drug tests and any other relevant information will be listed by treatment and subject.

Treatment

Use of concomitant medications and data on administration of study drug will be listed by treatment, and subject.

The number and percent of subjects with dose adjustments may be tabulated and the summary statistics for the study day at which the dose adjustment occurred provided by treatment.

Vital signs

All vital signs data will be listed by treatment, subject, and visit/time and if ranges are available abnormalities (and relevant orthostatic changes) will be flagged. Summary statistics will be provided by treatment and visit/time.

ECG evaluations

All ECG data will be listed by treatment, subject and visit/time, abnormalities will be flagged. Summary statistics will be provided by treatment and visit/time.

Clinical laboratory evaluations

All laboratory data will be listed by treatment, subject, and visit/time and if normal ranges are available abnormalities will be flagged. Summary statistics will be provided by treatment and visit/time.

Adverse events

All information obtained on adverse events will be displayed by treatment and subject.

The number and percentage of subjects with adverse events will be tabulated by system organ class and preferred term with a breakdown by treatment. A subject with multiple adverse events within a body system is only counted once towards the total of this body system and treatment. Separate tables and listings will be presented indicating event toxicity grade and study drug relationship.

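### Non-serious adverse events are recorded only to an end-of-study visit whose timing after early stopping is unsettled, and the crude percentages ignore time observed, so unequal stopping can understate a drug excess

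*Protocol*

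**What the plan says.** **When AE recording ends.** Protocol Section 9.1 defines an AE as an occurrence after consent "for participation in the study until the end of study visit". For later events thought to be related to treatment, it says: "This information must be recorded in the investigator's source documents; however, if the AE meets the criteria of an SAE, it must be reported to" the sponsor. Section 7.1 adds: "All patients should have a safety follow-up call conducted 30 days after last visit". Of that call it says "The information collected is kept as source documentation", and it requires only serious events (SAEs) to be reported. SAEs have a longer window under Section 9.2.2: "until 30 days [after the last study visit] must be reported to Novartis".

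**When the end-of-study (EOS) visit takes place.** Three passages bear on this.
- The design footnotes in Section 3.1 tie it to the last dose: "EOS evaluation to be completed approximately 28 days after the final study drug administration", which is Day 112 for a completer.
- Footnote 2 of the Section 8.1 schedule, written for patients who withdraw or stop study drug, says "the patient should be scheduled for a subsequent visit at which time all assessments at the EOS visit should be performed" and gives no interval.
- Section 7.2 keeps patients who stop treatment in the study unless they withdraw consent, and asks them back for the EOS visit if they can attend.

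**How AEs are summarised.** SAP Section 7.2 states: "The number and percentage of subjects with adverse events will be tabulated by system organ class and preferred term with a breakdown by treatment". Protocol Section 11.4.4 says the same by body system. The SAP adds tables by toxicity grade and by relationship to study drug. The visible text has no patient-time rate, no time-to-first-event summary and no common at-risk window.

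**The concern.** Safety and tolerability is a primary objective. Sections 6.6, 7.2 and 9.3 require treatment to stop for certain liver events, and Section 7.2 also for renal events, hypersensitivity and related Grade 3 events. The frequency of stopping can therefore differ between arms.

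A patient who stops early leaves AE observation sooner than a completer but still counts as one full patient in the denominator. The event that led to the stop is in the table. A different non-serious event that would have occurred later is not. If more LMB763 patients stop, the crude percentage for such events falls more on LMB763 than on placebo. A real excess on the drug is then understated.

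The unsettled EOS timing adds a second problem. Sites could schedule the visit differently and all be compliant, so the off-drug AE window for early stoppers could vary by site.

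**Working it through.** **Inputs from the documents.** Treatment runs to Day 84 and the completer's EOS visit is Day 112 (Protocol 3.1). Each cohort plans about 64 versus 32 patients, with about 81 of 96 completing, a loss of 1 − 81/96 = 15.6% (Protocol 3.1). Placebo patients are pooled across cohorts (SAP Section 4), which gives 64 versus 64 for one dose. The documents state no AE rate and no stopping rate by arm, so there is no figure of the plan's own to reproduce.

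**Assumed inputs.** 20% of LMB763 and 6% of placebo patients stop on Day 28. This implies 0.20 × 64 + 0.06 × 32 = 14.7 losses, close to the planned 15, but the split is hypothetical. The event has risk I over 112 days and a constant hazard, and is unrelated to the reason for stopping. Early stoppers are observed to Day 31 (visit 3 days later) or Day 56 (visit 28 days later).

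**Formulas.** Risk over t days: inc(t) = 1 − (1 − I)^(t/112). Crude proportion in an arm with stopping share s and stoppers observed for f days: (1 − s) × I + s × inc(f).

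**Equal hazards, I = 30%.** inc(31) = 9.40% and inc(56) = 16.33%.

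| EOS visit after stopping | LMB763 | Placebo | Gap | Ratio |
|---|---|---|---|---|
| 3 days | 0.80 × 30 + 0.20 × 9.40 = 25.9% | 0.94 × 30 + 0.06 × 9.40 = 28.8% | 2.9 points | 0.90 |
| 28 days | 0.80 × 30 + 0.20 × 16.33 = 27.3% | 0.94 × 30 + 0.06 × 16.33 = 29.2% | 1.9 points | 0.93 |
| Followed to Day 112 | 30.0% | 30.0% | 0 | 1.00 |

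For I = 10% the ratios are also 0.90 and 0.93.

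**A true excess.** Let the hazard ratio be 1.3 while on drug and 1 afterwards. Completers: 1 − 0.7^((1.3 × 84 + 28)/112) = 35.4%. LMB763 stoppers: 1 − 0.7^((1.3 × 28 + f − 28)/112), which is 11.8% at f = 31, 18.5% at f = 56 and 31.8% at f = 112.

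| Stoppers observed to | LMB763 | Placebo | Excess |
|---|---|---|---|
| Day 112 | 34.7% | 30.0% | 4.7 points |
| Day 56 | 32.0% | 29.2% | 2.8 points |
| Day 31 | 30.7% | 28.8% | 1.9 points |

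**Other assumed ranges.** Take equal hazards, 20% or 30% versus 10% stopping on Day 28 or 42, risks of 10%, 30% or 60%, and a visit 3 or 28 days after stopping. The higher-stopping arm then shows a percentage lower by 0.4 to 7.5 points. With 15.6% stopping at the same times in both arms the gap is 0.

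**Noise.** At a 30% rate the standard error of the difference is √(0.21 × (1/64 + 1/32)) = 9.9 points within a cohort, or √(0.21 × (1/64 + 1/64)) = 8.1 points with pooled placebo.

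**What a rate does.** Mean time at risk per patient (to the first event or the end of observation) is [(1 − s) × I + s × inc(f)]/h, with h = −ln(0.7)/112 = 0.00318 per day. For f = 31 the rates are 0.2588/81.3 days and 0.2876/90.3 days, both 3.18 per 1,000 patient-days. The bias disappears because the model has a constant hazard.

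**The case against.** The strongest reply is that the short window is only one reading. The design footnotes tie the EOS evaluation to the last dose, which would give an early stopper the same 28 off-drug days as a completer. Section 7.2 keeps stoppers in the study. Footnote 2 of the schedule does not say that the visit follows within days, and the 3-day gap is an assumption. This stands as far as it goes, but footnote 2 is the text written for stoppers and the passages do not agree. The 28-day reading also leaves total observation shorter: the 1.9-point gap above remains.

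A reader might infer that AEs of every kind cease to be recorded at the EOS visit. They do not, because SAEs are collected to 30 days after the last visit. Liver events are followed to resolution, and renal events to resolution or stabilisation.

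A reader might also infer that the arm with more stopping will look safer. The documents do not support that as a general result. It needs unequal stopping and later events of a different kind. In the hazard-ratio 1.3 example the drug still shows more events; its excess shrinks. Nor should a drug effect be carried to Day 112 as the benchmark, since dosing ends on Day 84 and Section 4.2 puts five half-lives at about 5 days.

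The study is non-confirmatory, the AE summaries are descriptive, and the gaps are well inside sampling error. All of this is true and limits the weight of the point. The error is nevertheless systematic, and crude tables do not show the unequal follow-up behind it. AE dates and dosing listings would allow rates later for events that were recorded. They cannot recover non-serious events that never reached the CRF.

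**Conclusion.** The point holds in a limited form. Non-serious AE recording stops at the EOS visit, the protocol does not settle when that visit occurs after early stopping, and the planned tables ignore time observed. If stopping is more frequent on LMB763, an excess of events other than the triggering one is understated.

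Under the assumed 20% versus 6% stopping on Day 28, equal hazards appear as a deficit of 1.9 to 2.9 points on the drug. A true excess of 4.7 points appears as 1.9 to 2.8. These sizes rest on an assumed split, a constant background hazard and stopping unrelated to the event counted. There is no bias if stopping is equal in frequency and timing. The point is worth correcting because safety is a primary objective and the correction is cheap, but the size is modest beside a standard error of 8 to 10 points.

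**What to change.** 1. **Protocol 3.1, 7.2, 8.1 (footnote 2) and 9.1.** Reconcile these passages so that AE recording for every dosed patient runs at least to 28 days after the last dose, the interval completers already get. Enter on the AE CRF any non-serious event reported at the existing 30-day call whose onset falls inside that window. The limit matters: a completer's call falls at about Day 112 + 30 = 142, after the window has closed.

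2. **SAP 7.2.** Beside each crude percentage, report follow-up time by arm and the number of patients with the event per patient-time at risk. Show on-treatment time (to a fixed, pre-stated lag after the last dose) separately from off-drug time. Mixing the two would dilute a drug effect, more so in the arm that stops earlier.

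Part 1 alone does not remove the effect of shorter total observation, so part 2 is also needed. The cost is a few more CRF entries and some added table columns, with no call beyond the one already planned. The rates remove the bias exactly only if the hazard is roughly constant; otherwise they still make the unequal follow-up visible.
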